11.1.2.1. Second Primary Malignancies

Second primary malignancies (SPM) will be monitored as adverse events of interest and reported in the CRF serious adverse event for SPM page throughout a subject's duration in the study (signing of informed consent form through the follow-up period of study). By-subject listings will be provided for SPMs and related procedures/surgeries, radiation therapies and regimen therapies.

SPM identified as treatment-emergent AESI will be summarized by treatment group.

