4.1.3 Follow-up Phase

All subjects discontinued from protocol-prescribed therapy for any reason will be followed for a period of 28 days following the last dose of IP or until the date of the last study visit, whichever period is longer, for the collection of AEs, concomitant medications and procedures, transfusions administered and healthcare resource utilization. Females of childbearing potential should avoid becoming pregnant for 3 months after the last dose of IP and male subjects should avoid fathering a child for 3 months after the last dose of IP.

All subjects discontinued from protocol-prescribed therapy for any reason will also be followed for survival, subsequent MDS therapies, progression to AML and second primary malignancy every month for the first year following Treatment Discontinuation and every three months thereafter until death, lost to follow-up, withdrawal of consent for further data collection.

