6.6.2 Progression to AML and Second Primary Malignancies

Progression to AML and second primary malignancies will be monitored as events of interest and should be included as part of the assessment of AEs throughout the course of the study. Investigators are to report progression to AML and any second primary malignancy, regardless of causal relationship to IP (oral azacitidine or placebo), occurring at any time from signing of informed consent until death, lost to follow-up, or withdrawal of consent for further data collection. Events of progression to AML and second primary malignancy are to be reported as a serious adverse event (SAEs; considered to be an adverse event of special interest (AESI) even if no other seriousness criteria apply). This information must also be documented on the appropriate pages of the CRF and in the subject's source documents. Documentation on the diagnosis of progression to AML and/or the second primary malignancy (eg, any confirmatory histology or cytology results, X-rays, CT scans, etc.) must be provided at the time of reporting as an SAE. Refer to [Section 11.2](#) for evaluation of AEs.

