11.5 Reporting of Serious Adverse Events

Any AE that meets any criterion for an SAE requires the completion of an SAE Report Form in addition to being recorded on the AE page/screen of the CRF. All SAEs must be reported to Celgene Drug Safety within 24 hours of the investigator's knowledge of the event by facsimile, or other appropriate method, using the SAE Report Form, or approved equivalent form. This instruction pertains to initial SAE reports as well as any follow-up reports.

Progression to AML and development of second primary malignancies will be monitored as events of interest and must be reported as SAEs regardless of the treatment arm the subject is in. This includes progression to AML or any second primary malignancy, regardless of causal relationship to IP (oral azacitidine or placebo), occurring at any time for the duration of the study, from the time of signing the ICD until death, lost to follow-up, or withdrawal of consent for further data collection. Events of progression to AML and second primary malignancy are to be reported using the SAE report form and must be considered an AESI even if no other serious criteria apply; these events must also be documented in the appropriate page(s) of the CRF and subject's source documents. Documentation on the diagnosis of progression to AML and/or the second primary malignancy must be provided at the time of reporting as an SAE (eg, any confirmatory histology or cytology results, X-rays, computed tomography [CT] scans, etc.).

The investigator is required to ensure that the data on these forms is accurate and consistent. This requirement applies to all SAEs (regardless of relationship to IP) that occur during the study (from the time the subject signs informed consent to 28 days after the last dose of IP or until the last study visit, whichever period is longer), and those made known to the investigator at anytime thereafter that are suspected of being related to IP. Serious AEs occurring prior to treatment but after informed consent will be collected.

The SAE report should provide a detailed description of the SAE and include a summary of hospital records and other relevant documents. If a subject died and an autopsy has been performed, copies of the autopsy report and death certificate are to be sent to Celgene Drug Safety

as soon as these become available. Any follow-up data will be detailed in a subsequent SAE Report Form, or approved equivalent form, and sent to Celgene Drug Safety.

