Oral azacitidine dose modifications due to nonhematological and hematological toxicities during oral azacitidine treatment should be managed as described in [Section 8.2.4](#) for dose modification guidelines due to toxicity.

Adverse Events

Adverse events (non-serious and serious) will continue to be collected in the EP AE CRF. Refer to [Section 11](#). Adverse Events for reporting requirements, responsibilities and procedures.

Concomitant Medications

All concomitant medications that are necessary for the subject's welfare may be given at the Investigator's discretion during the EP and recorded onto the CRF. However, treatment with any other investigational medication is not permitted. Refer to [Section 9](#) for prohibited concomitant medications/therapy for subjects on oral azacitidine.

Survival Follow-up

All subjects participating in the EP will be followed for survival, subsequent MDS therapies, progression to AML and secondary malignancy for 35 days \pm 7 days, including 28-day safety follow-up (refer to [Section 11.1](#): Monitoring, Recording, and Reporting of Adverse Events) following Treatment Discontinuation or until death, withdrawal of consent for further data collection, lost to follow-up, or study termination, whichever is earlier. The investigator must make every effort to obtain information regarding the subject's survival status before determining the subject is lost to follow-up.

Survival follow-up may be conducted via telephone contact with the subject, family, or the subject's treating physician or via record review (including public records, if admissible by law in the participating countries).

Monitoring of Subjects

The monitoring of subjects is as per the local standard of care, and at least:

- Complete blood count with WBC differential and platelet count as required, and at a minimum, prior to each dosing cycle
- For FCBP, pregnancy testing must be done prior to initiating a new cycle
- Bone marrow biopsy and aspirate as clinically indicated
- Additional tests or more frequent monitoring are at the Investigator's discretion based on the subject's clinical status.

Investigator's Responsibility

- Obtain subject's signature of the informed consent form to enter the EP phase
- Complete Extension Phase Case Report Form pages
- Document all adverse events (serious and non-serious) on the adverse event log page of the Extension Phase Case Report Form as required by the protocol ([Section 8.2.4](#))

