11.1. Adverse Events

Adverse events (AEs) will be coded according to the MedDRA version 21.0 or higher. The severity of AEs will be assessed by the investigator according to the Common Terminology Criteria for Adverse Events (CTCAE) version 4.0. For any AE not listed in the CTCAE grading system, the severity of these events will be assessed by the Investigator using a 5-point scale as described in Section 11.2.2. of the protocol.

Treatment-emergent adverse events (TEAEs) are defined as any AE occurring or worsening with an onset date on or after the date of the first dose of the study medication and within 28 days after the date of the last dose. AEs will be summarized by SOC, preferred term (PT) and treatment group. The AE summaries will include incidence tables of:

- Summary of TEAEs.
- TEAEs.
- Treatment-related TEAEs.
- Serious TEAEs.
- Treatment-related serious TEAEs.
- TEAEs with CTCAE toxicity grade of 3 or 4.
- Treatment-related TEAEs with CTCAE toxicity grade of 3 or 4.
- Serious TEAEs with severity of grade 3 or 4.
- Treatment-related Serious TEAEs with severity of grade 3 or 4.
- TEAE leading to death.
- TEAEs leading to dose reduction.
- TEAEs leading to dose interruption.
- TEAEs leading to dose interruption and reduction.
- TEAEs leading to treatment discontinuation.
- Treatment-related TEAEs leading to death.
- TEAEs by maximum severity.
- TEAEs by age group (<65, 65 to 74, ≥75 years).
- TEAEs by sex.
- TEAEs by decreasing order of frequency of preferred term.

- TEAEs by decreasing order of frequency of system organ class.
- Serious TEAEs by decreasing order of frequency of preferred term.
- Serious TEAEs by decreasing order of frequency of system organ class
- Pre-treatment AEs.
- Non-serious TEAEs

Subjects with multiple events reported for the same preferred term will be counted only once per SOC and PT level. For summaries by severity (CTCAE grade), if a subject experience the same PT multiple events, then the subject will be counted only once and for the greatest severity.

In summaries of treatment-related TEAEs, if a subject reports multiple occurrences of the same AE, only the treatment-related occurrence will be summarized. Adverse events with missing relationship to study medication will be imputed as related to study medication.

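### Second primary malignancies are collected through follow-up, but the SAP's only dedicated by-arm summary of them stops 28 days after the last dose

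*SAP*

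**What the plan says.** **Collection.** Protocol 6.6.2 requires SPMs to be reported, whatever their cause, "occurring at any time from signing of informed consent until death, lost to follow-up, or withdrawal of consent for further data collection". Protocol 11.5 repeats this for SAE reporting: "from the time of signing the ICD until death, lost to follow-up, or withdrawal of consent for further data collection". After treatment stops, Protocol 4.1.3 has subjects "followed for survival, subsequent MDS therapies, progression to AML and second primary malignancy every month for the first year following Treatment Discontinuation", and three-monthly after that. Table 1 of the protocol adds study closure as an end point. SAP 11.1.2.1 describes the same collection period: "signing of informed consent form through the follow-up period of study".

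**Analysis.** SAP 11.1.2.1 provides by-subject listings of SPMs and one summary by arm: "SPM identified as treatment-emergent AESI will be summarized by treatment group". SAP 11.1 defines treatment-emergent through the timing of the event: "onset date on or after the date of the first dose of the study medication and within 28 days after the date of the last", meaning the final administration of study drug. The exposure-adjusted incidence rate in the same section ends its person-time at death or last dose plus 28 days.

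**Later change.** The SAP was written for Amendment 5. Under Amendment 6, Appendix J has Extension Phase subjects "followed for survival, subsequent MDS therapies, progression to AML and secondary malignancy for 35 days", plus or minus 7 days, after treatment discontinuation.

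**The concern.** The period over which SPMs are sought and the period over which the arms are compared do not match. A non-fatal SPM diagnosed, say, three months or two years after the last dose is captured on the CRF and listed, but enters no planned count or rate by arm. A listing has no arm totals and no denominator, so a reader of the report could not judge from the tables whether late SPMs are balanced.

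The SAP treats comparable events more fully. Progression to AML is collected under the same reporting rule and gets a by-arm count (SAP 10.2.8) and a time-to-event analysis from randomization (SAP 10.2.9), neither limited to the treatment-emergent window. Deaths are tabulated by arm for both the on-treatment and post-treatment periods (SAP 11.2). Protocol 4.2 also justifies the placebo arm partly by the difficulty of recognizing short- or long-term side effects without a comparator. For non-fatal SPMs, the SAP uses that comparator only up to 28 days after the last dose.

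**Working it through.** **Inputs.** From Protocol 10.3: exponential OS with medians of 18 months (placebo) and 25.7 months (azacitidine), HR 0.70, uniform accrual over 56 months, 5% drop-out, 205 deaths, 108 subjects per arm. The primary analysis comes 12 months after the last subject is randomized, taken as month 68, so potential follow-up C is uniform on 12 to 68 months. Time on treatment is **an assumption**: the documents give only a recommended minimum of 6 cycles.

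**Step 1: reproduce the plan's own figures.** The documents state nothing on SPM at-risk time, so the check is on the survival model used below.

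- Power: Φ(√(205/4) × |ln 0.70| − 1.96) = Φ(2.553 − 1.960) = 72.4%, against the stated 72%.
- Deaths at month 68: with λ = ln 2/median, the mean of exp(−λC) is [exp(−12λ) − exp(−68λ)]/(56λ), which is 0.258 (placebo) and 0.373 (azacitidine). Deaths = 108 × (0.742 + 0.627) = 147.8 without drop-out, or 72% of 205. Multiplying by 0.95 gives 140.4, or 68%. The plan projects about 68%.

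**Step 2: share of follow-up inside the window if every subject stops after k cycles.** The window in months is W = [(k − 1) × 28 + 21 + 28]/30.4375. Without drop-out, and for W ≤ 12,

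share inside = [1 − exp(−λW)] / [1 − mean exp(−λC)].

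For k = 6, W = 189/30.4375 = 6.21 months.

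- Placebo: 0.2127/0.7417 = 28.7% inside, 71.3% outside.
- Azacitidine: 0.1542/0.6268 = 24.6% inside, 75.4% outside.

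For k = 24, W = 22.77 months, and the numerator becomes the mean of 1 − exp(−λ·min(W, C)): 0.5647 and 0.4422.

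| Cycles | W (months) | Outside, placebo | Outside, azacitidine |
|---|---|---|---|
| 3 | 3.45 | 83% | 86% |
| 6 | 6.21 | 71% | 75% |
| 12 | 11.73 | 51% | 57% |
| 24 | 22.77 | 24% | 29.5% |

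**Step 3: add drop-out and vary the shape of time on treatment.** This is a simulation at month 68, with drop-out as a competing hazard and the window running to last dose + 28 days. Each range covers OS medians of 18 to 25.7 months.

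| Time on treatment (assumed) | Share outside |
|---|---|
| Fixed, 6 cycles | 70-74% |
| Fixed, 12 months | 46-52% |
| Exponential, median 6 months | 63-67% |
| Exponential, median 12 months | 46-50% |
| Exponential, median 18 months | 36-40% |
| Exponential, median 24 months | 30-33% |

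With exponential time on treatment, half of the at-risk time falls outside when the median is about 10 months (OS median 18) to 12 months (OS median 25.7). Below that, more than half is outside; above it, less. Cut-offs after month 68 are not used for the size, because Amendment 6 shortens SPM follow-up for Extension Phase subjects.

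**The case against.** Five points can fairly be made in the SAP's defence.

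- **Late SPMs are not lost.** They are in the SPM listings and in the protocol's listing of SAEs at any time (Protocol 10.7). SAP 11.2 also tabulates cause of death and primary diagnosis by arm, including post-treatment deaths, so a fatal late SPM can be counted there. This stands. The gap is a by-arm count or rate for late non-fatal SPMs, and a reader who infers that every late SPM appears only in a listing goes too far.
- **Unequal time on treatment is partly handled.** A reader might say that the truncated percentages are not like for like. The exposure-adjusted rate in SAP 11.1 covers all treatment-emergent events by SOC and preferred term, so it addresses this inside the window. It does nothing beyond it.
- **The protocol may already require more.** Protocol 10.7 says that AESIs are to be summarized and sets no treatment-emergent limit there, and SAP 16 lists no change on this point. On that reading the SAP narrows the protocol without saying so. That is a further reason to reconcile the two; it does not supply the missing table.
- **The SAP allows additional safety analyses.** It does (SAP 11 and 11.1.2), but at discretion and without naming SPMs.
- **The documents do not call SPM a delayed risk.** They name it as an event of interest and give no such reason. Long collection suggests interest in late events, but that is inference. No SPM rate is given either, so a share of person-time cannot be turned into a number of missed cases.

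**Conclusion.** The point holds as a gap in descriptive safety reporting. SPMs are collected well past treatment, the only dedicated by-arm summary ends 28 days after the last dose, and late non-fatal SPMs are in no by-arm table.

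Its size is conditional. At the primary analysis, under the plan's OS and accrual assumptions, the share of at-risk time left out is about 70-75% if all subjects stop after 6 cycles, about half with 12 months of treatment, and about 24-33% with roughly 24 cycles or a 24-month median. A reader might infer that most of the at-risk time is always excluded. The documents do not support that, because they give no expected or observed time on treatment and the answer crosses one half within a plausible range.

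The long collection period also needs one qualification: under Amendment 6, follow-up for SPM in the Extension Phase ends 35 ± 7 days after discontinuation. That came after the SAP and after the primary data cut-off of 25-Jan-2019, so it limits later analyses only. Nothing here touches the primary endpoint, OS or the control of type I error.

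**What to change.** In SAP 11.1.2.1, add a by-arm summary of all SPMs in the safety population from first dose to the last SPM follow-up contact:

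- Give the number of subjects with at least one SPM and the rate per 100 person-years.
- End each subject's person-time at first SPM, death or last contact. For Extension Phase subjects under Amendment 6, last contact is the end of the shortened follow-up. Time after a first SPM should not stay in the denominator; the SAP's existing exposure-adjusted rate already stops at first occurrence.
- Keep the treatment-emergent count as a subset row.
- Show onset before and after the start of subsequent MDS therapy, splitting person-time at the same date. Splitting only the cases would leave the two rates unreadable.

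The cost is one descriptive table from data already collected: the SPM CRF page, follow-up contacts and subsequent therapies. The primary clinical study report is final, so the table would go into an addendum or be reported with the separate final analysis of OS and AML. The downside is small: late cases may be confounded by subsequent therapy, and the split makes this visible without removing it.

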11.1.2.2. Progression to AML

Progression to AML will be identified as treatment-emergent AESI and will be summarized by treatment group.

11.2. Death

Frequency tables of primary cause of death category (as selected by the investigator), and the primary diagnosis (by SOC and PT) per the death CRF page will be provided by treatment period (on-treatment, or post-treatment) by treatment group for subjects in the safety population, as well as for subjects who are screen failures (pre-treatment period). A listing of deaths from the death CRF page, will be provided for all subjects who died after signing informed consent.

11.3. Clinical Laboratory Evaluations

Clinical laboratory values will be presented using the reported units. Change in clinical laboratory results from baseline (last non-missing value on or prior to the date of first dose of the study drug) to each scheduled time point will be provided for the safety population. Clinical laboratory values will be graded according to CTCAE version 4.0 for applicable tests. Shift tables for change in maximum CTCAE grades of high and low lab values, separately, will be provided for the safety population by treatment for those labs that have CTCAE grades. Separate shifts tables will be provided for lowest value by cycle and highest value by cycle. Clinically significant laboratory abnormalities that meet Grade of 3 or Grade 4 criteria according to the CTCAE will be listed and summarized (counts and percentages) by cycle. Laboratory data collected after the date of the end of treatment visit, last dose date + 28 days, whichever the latest, will not be used for summary. Nadirs, the minimum values, of selected hematology parameters, ie. Hgb, platelets, absolute neutrophil count (ANC), white blood cell counts, and RBC, across all cycles and within each cycle will be summarized. The day of nadir will be summarized categorically by frequency of the day of the cycle that the nadir observation occurs, by cycle and treatment. The categories for the days within a cycle are day 1-7, Day 8-14, Day 15-21 and Day >21. The average onset day of nadir across all cycles, the analyte value at nadir by cycle, and the change from baseline to analyte value at nadir will be summarized descriptively by treatment for each selected hematology test.

A separate listing, including only values outside the normal range, if any, will also be provided. A listing of all clinical laboratory values will be provided. Separate listings will be provided for the hematology, blood chemistry, coagulation, urinalysis, erythropoietin, ferritin and serum transferrin saturation laboratory values.

Graphical display of select laboratory parameters over the course of the study will be provided (if needed).

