6.6.5 Hematology and Serum Chemistry Laboratory Evaluations

Hematology and serum chemistry laboratory analyses must be performed according to [Table 1](#). The same parameters as required at screening should be evaluated (see [Section 6.1](#) for details regarding the parameters for hematology and serum chemistry, respectively).

The hematology samples will be collected prior to IP administration and will be analyzed by the central laboratory. The frequency of hematology assessment in the treatment phase is as such: weekly on Day 1, 8, 15 and 22 in Cycles 1-2, and biweekly on Day 1 and 15 in Cycles 3-12, and monthly on Day 1 thereafter and at Treatment Discontinuation.

The serum chemistry samples will be collected prior to IP administration and will be analyzed by the central laboratory. The frequency of serum chemistry assessment in the treatment phase is as such: weekly in Cycles 1-2 and monthly on Day 1 thereafter, and at Treatment Discontinuation.

On a case-by-case basis and at the investigator's discretion, the Day 8, 15, and 22 hematology and serum chemistry draws may be performed at the subject's local/primary physician office and shipped to the central laboratory for analysis or obtained via an in-home nursing service (where

available). In these specific cases, the sponsor needs to be consulted prior to performing these blood draws to assess logistics and obtain local laboratory details. In addition, to ensure the medical care of the individual study subject is maintained, the investigator remains responsible for all subject procedures performed during the study and communication with the subject must be continued. Proper documentation is required in the source documents at the investigative site in these cases.

Any or all laboratory assessments may be repeated more frequently if clinically indicated. In the event that an immediate laboratory assessment is required to acutely manage a subject, local laboratory tests may be used. In addition to collecting the local laboratory sample, a second sample should be collected and sent to the central laboratory.

Refer to [Section 11.3](#) for guidance on abnormal laboratory values and test results.

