8.2.4 Dose Modifications

All subjects in Cycle 1 or 2 will receive CC-486 for 14 days of a 28-day cycle schedule. Subjects may increase to a 21-day schedule (Level +1) at the conclusion of Cycle 2 if no Grade 3 or 4 toxicities requiring dose delay or reductions and if no evidence of hematological improvement upon discussion and agreement between the investigator and the Medical Monitor.

When the dose level is adjusted, weekly hematology monitoring is required for 2 cycles including the cycle in which the adjusted dose or dosing schedule was applied as well as the following cycle, see Section 8.2.5 Re-treatment Criteria.

The dose/treatment schedule modifications steps for 14 days schedule are:

	Dose/schedule		
	300 mg/21d		Level +1
Dose escalation step	300 mg/14d		Level 1
Dose escalation step	200 mg/14d	Dose reduction step	Level -1
Dose escalation step	200 mg/7d	Dose reduction step	Level-2

All efforts should be made to dose IP according to schedule without cycle delay, dose interruption and reduction. Subjects will be monitored for hematologic toxicity and non-hematologic toxicity with the National Cancer Institute (NCI) Common Terminology Criteria for Adverse Events (CTCAE, Version 4.0) used as a guide for the grading of severity.

If a certain level of toxicity is observed (eg, [Table 2](#)) and considered by the investigator to be at least possibly related to treatment, IP dosing may be interrupted, delayed or modified. The investigator may contact the Medical Monitor prior to any treatment adjustment. Please note that in the event neutropenia Grade 4 is observed, or any adverse event that would put a subject at unacceptable risk in the investigator’s opinion, IP dosing may be interrupted, delayed or modified even if not considered by the investigator to be at least possibly related to treatment.

A maximum of one dose reduction step to 200 mg is permitted in the event of toxicity. A maximum of two treatment schedule modifications, stepwise first from 21 to 14 days and then from 14 days to 7 days, at a dose of 200 mg once a day are permitted in the event of continuing toxicity. Subjects are not allowed to receive less than 200 mg IP or be scheduled to receive treatment for less than 7 days.

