5.1.3. Calculation of Cycles

The start date of each treatment cycle will be calculated based on study drug exposure records (with non-zero dosing) for each patient. The start date of the first cycle (S_1) will be the date when the subject receives the first dose of study drug.

Once the start dates, *e.g.*, S_1, S_2, S_3, \dots are calculated, the end date of each cycle is calculated as the day before the start date of the following cycle, *i.e.*, $E_i = S_{i+1} - 1, i=1, 2, \dots$. For the last cycle, the end date will be calculated as the cycle start date plus prescribed cycle length (28 days), or the death date, whichever is earlier. The cycle number for each date of interest, *e.g.*, AE or lab, will be calculated based on the cycle window set by their start and end dates. If a date is on or after S_i and before S_{i+1} , the corresponding cycle number will be *i*. For AEs or lab results which meet the treatment-emergent criterion or reporting criterion, the events or results after the end date of the last cycle will be included in the summary of the last cycle.

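### SAP 11.3 tabulates day of nadir for every cycle, but outside the weekly-sampled cycles the result mainly reflects when blood was drawn

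*SAP*

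**What the plan says.** **Summaries planned (SAP 11.3).** The section covers "Nadirs, the minimum values, of selected hematology parameters": hemoglobin, platelets, ANC, WBC and RBC, both overall and within each cycle. On timing it states "The day of nadir will be summarized categorically by frequency of the day of the cycle that the nadir observation occurs", broken down by cycle and treatment. The bins are fixed: "The categories for the days within a cycle are day 1-7, Day 8-14, Day 15-21 and Day >21". A pooled figure is added: "The average onset day of nadir across all cycles". There is no minimum number of counts per cycle and no restriction to particular cycles. Baseline is the last available value up to and including the day of first dose.

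**Sampling schedule (Protocol 6.6.5).** Hematology is drawn before dosing. The timing for the first 12 cycles reads "weekly on Day 1, 8, 15 and 22 in Cycles 1-2, and biweekly on Day 1 and 15 in Cycles 3-12". From Cycle 13 the only routine in-cycle count is on Day 1, with one more when treatment is discontinued. Further counts are allowed when clinically indicated.

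**Cycle assignment (SAP 5.1.3).** For a date on or after the start of cycle *i* and before the start of the next cycle, "the corresponding cycle number will be" *i*.

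**Exceptions to the routine schedule.**
- Protocol 8.2.4 (repeated in 8.2.5): after a dose-level adjustment, "weekly hematology monitoring is required for 2 cycles including the cycle in which the adjusted dose or dosing schedule was applied" and the cycle after it. The dosing table in 8.2.4 labels the move to the 21-day schedule after Cycle 2 as Level +1.
- Protocol 8.2.5: samples needed to release the next cycle should be drawn ahead of its start.
- Protocol Table 1, footnote a: visit windows are ±3 days in Cycles 1-2 and ±7 days from Cycle 3.

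**The concern.** A day-of-nadir table is informative only if counts are taken on enough days for the minimum to fall in any of its bins. The routine schedule meets that condition in Cycles 1-2 and stops meeting it at Cycle 3, while the SAP keeps the same four bins throughout and then averages across all cycles.

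The Day 1 count adds a separate problem. It is taken before that cycle's drug, yet SAP 5.1.3 places it in the cycle it opens, so it competes to be that cycle's nadir. Protocol 8.2.5 uses the same count differently: after hematotoxicity it is set against the previous cycle's nadir to judge recovery. In Cycle 1 one pre-dose value can be both the baseline and the nadir, which gives a change from baseline to nadir of zero.

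The timing of myelosuppression matters in this trial. Protocol 1.4.1 reports an imbalance in deaths, with infection the leading cause among subjects on oral azacitidine. A reader comparing nadir day across cycle blocks could take a change in visit frequency for a change in tolerance.

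**Working it through.** The plan states no figure to reproduce. The check maps scheduled draws to bins and then works the pooled average.

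**Step 1. Bin coverage on nominal days** (draw days from Protocol 6.6.5, bins from SAP 11.3; the gap is measured to the next scheduled count, taking the next cycle's Day 1 as Day 29).

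| Cycles | Scheduled days | Bins reached | Largest gap |
|---|---|---|---|
| 1-2 | 1, 8, 15, 22 | 4 of 4 | 7 days |
| 3-12 | 1, 15 | 2 of 4 (1-7, 15-21) | 14 days |
| 13 on | 1 | 1 of 4 (1-7) | 28 days |

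**Step 2. Effect of the visit window.** In Cycles 3-12 the Day 15 count may fall from 15 − 7 = Day 8 to 15 + 7 = Day 22. It can land in Days 8-14, 15-21 or >21, but which one depends on the appointment date.

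**Step 3. Average onset day over 12 cycles.** Assume nominal days, the routine schedule, a nadir on the same day in every cycle, and Day 15 as the lower of the two counts in Cycles 3-12.
- True Day 22: (2 × 22 + 10 × 15)/12 = 194/12 = 16.2, which is too early.
- True Day 15: (2 × 15 + 10 × 15)/12 = 15, which is correct.
- True Day 8: (2 × 8 + 10 × 15)/12 = 166/12 = 13.8, which is too late.

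**Step 4. Illustrative simulation.** The assumptions are not from the documents: a V-shaped log count, a 50% fall, full recovery by Day 29, log-scale noise with SD 0.15, and a true nadir on Day 10, 15, 18, 22 or 25.
- Cycles 1-2: the most frequent reported bin was the true bin in all five scenarios and held 54-91% of subjects.
- Cycles 3-12, nominal days: 97-100% were reported in Days 15-21, wherever the true nadir lay.
- Cycles 3-12, visits spread evenly over ±7 days: 42-46% in Days 8-14, 45-46% in Days 15-21 and 6-7% in Days >21, with almost no relation to the true day.
- Cycle 13 on, Day 1 count only: 100% in Days 1-7, and none of the within-cycle fall captured.

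**The case against.** The strongest reply is that the SAP promises only observed minima, which can be computed in any cycle with a count, and that the by-cycle layout leaves Cycles 1-2 readable on their own. Protocol 1.4.1 places most deaths on oral azacitidine in the first 56 days, nominally Cycles 1-2 (2 × 28), where the bins are covered. SAP 11.3 also gives changes at scheduled time points, Grade 3 or 4 abnormalities by cycle and full listings, and SAP 11.1.1 gives adverse events by cycle and cycle day. All of this stands. It limits the consequence, but it does not make the later-cycle timing or the pooled average interpretable.

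Four stronger readings are tempting, and the documents do not support them.
- *The summaries cannot be derived.* They can. The fault is in reading them as true nadirs.
- *Every subject is affected from Cycle 3, and from Cycle 13 the Day 1 count is the only candidate.* Weekly counts follow any dose-level change, in any cycle, and on a plain reading cover Cycles 3-4 after the Level +1 step-up. Unscheduled and discontinuation counts add more. A sample drawn before the cycle starts belongs, under SAP 5.1.3, to the previous cycle, normally as Day >21.
- *The tables will show the nadir moving earlier and becoming shallower.* The documents do not say when the true nadir occurs, and Step 3 gives errors in both directions. Dosing may also rise from 14 to 21 days after Cycle 2, so the observed depth in later cycles cannot be predicted.
- *The arms will differ.* No adjustment rates by arm are given. The Grade 4 neutropenia rules apply whether or not the event is related to study drug, and the step-up requires both freedom from limiting toxicity and no hematological improvement, which could favour denser sampling on placebo. A difference is possible, but its direction is unknown.

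**Conclusion.** The point holds for subjects on the routine schedule. In Cycles 1-2 the reported bin is meaningful to about a week. From Cycle 3 it mainly records the draw date, and where Day 1 is a cycle's only count it says nothing about that cycle's drug effect. The pooled onset day mixes three sampling densities. In the 12-cycle illustration it is 5.8 days too early for a true Day 22 (22 − 16.2) and 5.8 days too late for a true Day 8 (13.8 − 8).

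The exceptions make sampling more uneven across subjects. If their frequency differs by arm, the by-treatment nadir comparison is affected too. The size rests on nominal visit days and an assumed true nadir day; the bin coverage rests only on the documents. This is descriptive safety output, and neither the primary endpoint nor overall survival is touched. It is worth correcting because the correction is cheap and the misreading is easy.

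**What to change.** Amend SAP 11.3 as follows.
1. Limit day of nadir and average onset day to Cycles 1-2, where weekly counts are scheduled for all subjects.
2. Do not let a pre-dose Day 1 value count as a nadir of the cycle it starts. In Cycle 1 it is baseline only; in later cycles treat it as the end of the preceding cycle.
3. For later cycles keep the minimum, label it *lowest observed value*, and show the number of counts per cycle by arm.

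Dropping later-cycle minima, or showing only Day 15 in Cycles 3-12, is not needed and would discard low counts that were actually observed.

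**Cost.** SAP wording and simpler tables, with no new data. There would be no nadir-timing summary after Cycle 2. With Day 1 excluded, the Days 1-7 bin in Cycles 1-2 would be filled only by unscheduled counts or by a Day 8 visit brought forward within its window, and a footnote should say so. The Amendment 6.0 rationale states that the primary-analysis report is already final, so for those tables the change means a re-run or an explanatory note.
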